initiating traditional psychotherapy between 12 to 24 weeks in patients in PS-cCBT versus EUC who have continued significant depressive symptoms at 12 weeks, defined as IDS-SR >16. The likelihood of initiation of traditional psychotherapy by 24 weeks will be compared using logistic regression model. As patients in need of continuing treatment at 12 weeks from the two groups are likely to differ, the model will be adjusted for variables that show meaningful differences between groups at 12 weeks. Although completion of a traditional therapy trial will be of interest, our primary interest here will be to see whether PS-cCBT increases the likelihood that Veterans would initiate a traditional therapy.

E.11.d Secondary Aim: Mediation of Intervention Effects on Symptoms, Functioning, QoL: We will examine whether any improvements in the primary outcomes of depressive symptoms, quality of life, functional status, or recovery focus are mediated through increased medication adherence or increased depression coping skills. To test whether a variable might be a mediator, we will first test the associations between the intervention and the mediator, and then the mediator and the outcome of interest using bivariate analyses. A variable will be considered a potential mediator if the variable is associated with both the intervention and the outcome in these analyses (i.e., as determined by a significance level of $P < .10$), and changes in the mediating variable occur prior to changes in outcomes.

Finally, for primary outcomes, such depressive symptoms at 24 weeks, we will additionally include the change in depression coping score from baseline to 24 weeks and/or change in antidepressant adherence from baseline to 24 weeks. If, as hypothesized, the intervention's effects on the primary outcomes are mediated through changes in depression coping or increased antidepressant adherence, the variance in 24 week symptoms explained by the intervention group will be less once the depression coping scores and antidepressant adherence are taken into account. We will also consider change in depression coping score from baseline to 12 weeks and/or antidepressant adherence at 12 weeks as potential mediators as the early effect of intervention on these variables may have affected the 24 week outcome.

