We propose to enroll 330 patients in total (165 per group). The sample size was calculated to provide 90% power to detect a difference in levels of depressive symptoms at the primary end-point of 24 weeks, conservatively assuming a mean effect size of 0.4 SD with a two-tailed alpha of .05 and 20% dropout. We expect that this effect size is conservative based on the meta-analysis completed by Spek et. al. The meta analysis of cCBT interventions for depression and anxiety found that RCTs of cCBTs for depression and anxiety with therapist support had a mean effect size of 1.00 SD, while unsupported cCBT had a mean effect size of 0.26 SD. This suggests that we can reasonably expect our peer-supported cCBT to have an effect size in the range of 0.4 to 0.6 SD compared with enhanced usual care. In another study, Titov et al, reported an effect size of 1.1 from a technician supported cCBT for depression. In our pilot work, congruent with reported effect sizes in the literature in other populations, we found that depressive symptoms among Veterans with depression enrolled in BTB were reduced by 27%, with a mean BDI-II of 21.9 (SD=11.1) at baseline and 16 (SD=13.5) at 8 weeks. Although the pilot study did not have a control group and the endpoint was at 8 weeks, the effect size estimated based on changes from baseline to 8 weeks can be considered to range from 0.43 SD (with an assumed SD of 13.5) to 0.53 SD (an assumed SD of 11.1). Thus, based on the meta-analyses and our pilot data, we consider a between-group difference of 0.4 SD a clinically meaningful and detectable effect size for the proposed intervention. We also note that for the analysis using longitudinally measured data, the power will also depend on the within-person correlation. The proposed sample size, however, will likely give greater power than 90% if 0.4 SD is the time-averaged between-group difference.

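### E.11.d screens the mediator–outcome link without treatment arm and confirms it by an unquantified fall in variance explained, so a variable that only responds to treatment can be read as a mediator

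*Combined protocol and SAP*

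**What the plan says.** Section E.11.d asks whether gains in the primary outcomes run through antidepressant adherence or depression coping skills. The procedure has two stages.

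- **Screen.** First, "we will first test the associations between the intervention and the mediator"; second, "and then the mediator and the outcome of interest using bivariate analyses". Then: "A variable will be considered a potential mediator if the variable is associated with both the intervention and the outcome in these analyses", each at P<.10. The same sentence adds a third condition, that change in the mediator comes before change in the outcome. No test or operational rule is given for it.
- **Confirmation.** Changes in coping and/or adherence from baseline to 24 weeks are added to the model for the 24-week outcome. If mediation holds, "the variance in 24 week symptoms explained by the intervention group will be less once" these variables are taken into account. Change to 12 weeks is mentioned as a further option.

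The outcome models in E.11.b contain arm, the baseline outcome and site. No section gives an arm-adjusted criterion for the mediator–outcome path, an indirect effect, an interval, or a size of fall that would count. The outcome table in E.11.b lists two coping scales (DCSES and CBTSQ), so with adherence there are about three candidates.

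**The concern.** If treatment improves both coping and symptoms, the two are correlated across the whole sample through arm alone, even when coping has no effect on symptoms. A crude test of coping against symptoms therefore rejects more often than its nominal 10%, and increasingly so as the programme moves coping more.

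The second stage should catch this but is poorly suited to it. Arm and a treatment-responsive variable share variance, so adding the variable tends to reduce arm's unique share whether or not it mediates. A smaller share is what mediation predicts, but it is also what mere correlation with arm predicts.

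The temporal condition could help, but it is undefined, and the main mediator window (baseline to 24 weeks) is the same as the outcome window.

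At stake is a named secondary aim: how PS-cCBT works. Unlike the subgroup analyses in E.11.e, it carries no caveat that it is exploratory.

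**Working it through.** **Inputs from E.13.** Enrolment is 330, or 165 in each arm. Target power is 90% for the depressive-symptom comparison. The assumptions behind it are given as: "conservatively assuming a mean effect size of 0.4 SD with a two-tailed alpha of .05 and 20% dropout". The expected effect could "have an effect size in the range of 0.4 to 0.6 SD compared with enhanced usual care".

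**Reproducing the plan's sample size.** n per arm = 2(1.960 + 1.282)²/0.4² = 131.4, so 132. Dividing by 0.8 for dropout gives 165 per arm, 330 in total. The figure reproduces, and 132 completers per arm (264 in all) is used below.

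**Assumption.** The documents give no expected effect on coping or adherence. The mediator shift *a* is therefore set at 0.3, 0.5 and 0.8 SD. The mediator has no effect on the outcome, and the two are uncorrelated within arm.

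**Step 1: crude correlation created by arm.** With outcome effect d = 0.4, r = (a·d/4)/√[(1 + a²/4)(1 + d²/4)].
- a = 0.3: 0.03/√(1.0225 × 1.04) = 0.029
- a = 0.5: 0.05/√(1.0625 × 1.04) = 0.048
- a = 0.8: 0.08/√(1.16 × 1.04) = 0.073

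Multiplying by √264 = 16.25 gives expected z of 0.47, 0.77 and 1.18. The two-sided .10 test (critical value 1.645) then rejects in about 14%, 20% and 32–33% of trials. Simulation gives 13.8%, 19.8% and 32.7%. With arm in the model the rate is 10%.

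**Step 2: why the variance falls anyway.** Arm's unique variance after adding M is (r_XY − r_MY·r_XM)²/(1 − r_XM²). With no mediation, r_MY = r_XM·r_XY in expectation, so this equals r_XY²(1 − r_XM²). A fall of the fraction r_XM² = (a²/4)/(1 + a²/4) is built in: 0.0225/1.0225 = 2%, 0.0625/1.0625 = 6% and 0.16/1.16 = 14%. In simulation, among non-mediators that pass the screen, arm's explained variance falls in about 91–92%, 96% and 99% of trials.

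**Step 3: the whole rule.** Simulation without covariates, 20,000 trials per scenario, d = 0.4. Repeat runs moved these figures by less than one percentage point. Percentage of trials declaring a non-mediator:

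| Rule | a = 0.3 | a = 0.5 | a = 0.8 |
|---|---|---|---|
| E.11.d, any fall counts | 10.6 | 19.0 | 32.4 |
| E.11.d, fall of at least 30% required (assumed threshold) | 1.4 | 5.5 | 18 |
| Joint test, arm-adjusted, .10 on both paths | 8.0 | 9.7 | 10.3 |
| Joint test, arm-adjusted, .05 on both paths | 3.3 | 4.7 | 5.0 |

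Adding baseline outcome and site to the final model gives 10.5%, 18.2% and 32.0% for the first row. At d = 0.6, the top of the expected range, that row becomes 15%, 30% and 54%. For at least one of three independent non-mediators at d = 0.4 it is 29%, 45% and 65%.

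**Step 4: separating alpha from arm omission.** Comparing the first and third rows holds alpha at .10. The excess is 10.6 − 8.0 = 2.6 points, 19.0 − 9.7 = 9.3 points and 32.4 − 10.3 = 22.1 points.

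**Step 5: confounding.** With a = 0.5 and a within-arm mediator–outcome correlation of 0.2 from a common cause, E.11.d declares mediation in 98% of trials and the arm-adjusted .05 joint test in 89%.

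**The case against.** The strongest reply is that the rule is less lax than the simulation makes it. Four parts of that reply have force.

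- A reader might infer that the whole procedure ignores arm. It does not: the first screening test is arm against mediator, and the final model contains arm. Only the mediator–outcome screen omits it.
- The temporal condition is part of the rule and gets no credit in the figures. Enforced, it could only lower them.
- The plan calls a screened-in variable a potential mediator and says what mediation would predict. It does not say that any fall, however small, proves mediation. Under a 30% requirement the rates drop to 1.4%, 5.5% and 18%. That threshold is an assumption, but so is counting any fall.
- Part of the gap from a conventional .05 test is the looser alpha. At a 0.3 SD shift that accounts for most of it.

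These points limit the size of the problem without removing it. The plan states neither a temporal test nor a threshold, so nothing in it commits the analyst to the stricter version.

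A reader might also infer that the P<.10 arm screen loses modest true mediators and that a modern rule would recover them. This is not shown. For a 0.3 SD shift the expected z is 0.3 × √(132/2) = 2.44. A .10 test misses it about 21% of the time, and an unadjusted .05 test of the same path about 32%.

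**Conclusion.** The defect stands in a bounded form. The mediator–outcome screen omits arm, and the confirming criterion has no threshold, test or interval and barely filters if any fall counts. At the planned 0.4 SD effect, a single variable that only responds to treatment would be declared a mediator in up to about 10%, 19% or 32% of trials for assumed shifts of 0.3, 0.5 or 0.8 SD. The part due to omitting arm is small at 0.3 SD and large at 0.5–0.8 SD.

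It would go too far to say that the plan will often produce false mediators, or that these percentages are its actual error rate. They are upper bounds, and they depend on mediator shifts that the documents do not give. Nor would adjusting for arm alone make a mediation claim safe, since the 3–5% figure assumes no common cause of coping and symptoms within arm.

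This should be changed before analysis. It concerns a secondary aim; the primary comparison and the sample size are untouched.

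**What to change.** Replace the P<.10 screen and the variance-falls criterion in E.11.d. For each named mediator (each coping scale, and antidepressant adherence):

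1. Fit the 12-week mediator on arm, baseline mediator and site.
2. Fit the 24-week outcome on arm, 12-week mediator, baseline mediator, baseline outcome, site and the measured baseline variables thought to affect both mediator and outcome. List those variables in advance.
3. Report the indirect effect (product of the arm–mediator and mediator–outcome coefficients) with a bootstrap 95% confidence interval for every mediator, whatever its significance.
4. Add a sensitivity analysis for unmeasured mediator–outcome confounding.
5. Describe an interval that excludes zero as consistent with mediation if there is no unmeasured confounding, and not as proof of mediation.

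Using the 12-week mediator gives the temporal condition a concrete form, and that assessment is already scheduled. The cost is revised SAP wording, standard code and a little more analysis; no new data are needed. The trade-off is a lower chance of declaring mediation than under the present rule. The change should not be presented as recovering modest true mediators.

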The PS-cCBT intervention and enhanced usual care (EUC) will be delivered over 12 weeks. The Beating The Blues (BTB) program consists of 8 interactive modules and recommends completing one module per week. However, we will provide 12 weeks of peer specialist support for completion of these 8 modules. Table 3 lists the components that will be delivered in each of the study treatment arms.

Table 3: Components of Treatment Arms

Enhanced Usual Care	PS-cCBT Intervention

 • Usual depression care • Patient education regarding treatment options, including antidepressants and evidence-based psychotherapies • Bi-weekly mailings with depression self management tips and local resources • Notification to the primary care clinician at 12 and 24 weeks if patient shows significant clinical worsening 	
 • Usual depression care • Access to cCBT program—Beating the Blues • Veteran peer specialist assigned • Peer specialist contacts at least once per week for 12 weeks (in-person or by telephone) to provide support and encourage cCBT participation and completion • Notification to the primary care clinician at 12 and 24 weeks if patient shows significant clinical worsening

E. 6.a Enhanced Usual Care:

As outlined above, in 2010, primary care patients newly diagnosed with depression in the study primary care settings (AA, DET, and BC and associated CBOCs) received the following treatments. Approximately 70% received an antidepressant fill, and 51% of these patients (36% overall) had an adequate trial of antidepressant (84 or days supply of antidepressant in the 114 days after first AD fill). Approximately 22% of patients had one psychotherapy visit within 14 weeks of their depression diagnosis and 3% had 8 or more psychotherapy visits within the 14 weeks following their depression diagnosis.

We assume that usual care delivered to our EUC patients will be similar to that outlined above, although our enhancements to usual care may increase treatment use slightly. (We provide these enhancements to increase the credibility and acceptability of usual care for patients randomized to this arm, please see Section E.7.)

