Inventory of Depression Symptoms – Self Report (IDS-SR) is a 31-item self-report instrument for measuring the severity of depression symptoms among adults. Each item is rated on a four-point scale (0-3), and aggregate scores range from 0-84. The IDS-SR has been shown to be reliable, with Cronbach’s α ’s in the range of 0.92-0.94 (Rush et al., 1996).

Veterans RAND 12-Item Health Survey (VR-12) is a measure of functional status adapted from the Medical Outcomes Study Short Form-36 for use among Veterans. The measure assesses physical functioning (PF), role limitations due to physical problems (RP), bodily pain (BP), general health perceptions (GH), energy/vitality (V), social functioning (SF), role limitations due to emotional problems (RE), and mental health (MH). The VR-36 has somewhat greater precision at the lower end of the health status continuum than the SF-36. The VR-12 has been used in quality management systems in the VHS (Kazis et al., 2006).

The Quality of Life Enjoyment and Satisfaction Questionnaire Short Form (Q-LES-Q-SF) is a valid proxy for the longer Q-LES form. It consists of 14 items that patients rate on a 5-point scale to indicate their satisfaction with a variety of life domains, including physical health, mood, work, household activities, social relationships, etc.(69) The Q-LES-Q-SF has been shown to have high levels of reliability and has been used in numerous studies of depression, including the NIMH funded STAR*D study.(69)(70)(71)

Recovery Assessment Scale - Short Form (RAS-SF): This 20-item scale is a shorter version of the RAS(72) and has four factors: personal confidence and hope, willingness to ask for help, reliance on others, and no domination by symptoms. The RAS-SF shows evidence for both convergent and discriminant validity when compared to quality of life, social support, and symptomatic scales. (73)

Alcohol Use will be assessed using the *Alcohol Use Disorders Identification Test (AUDIT-C)* which assesses average alcohol consumption (quantity and frequency) and binge drinking (6 or more) over the past 3-months.(84) Recent literature support the internal consistency, test-retest reliability, and accuracy of the AUDIT-C in identifying at-risk alcohol use.

E.9.b Secondary Outcomes

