We have attempted to keep the burden of study assessments within reason, deliberately choosing some shorter measures of important constructs, if possible. (For example, we use the GAD-7 rather than the BAI for measurement of anxiety because of its shorter length.) The estimated times for study assessments is approximately 50-60 minutes, based on published questionnaire administration times and the use of the general rule of 5 closed-ended questions or 2 open-ended questions per minute.

The Interpersonal Support Evaluation List (ISEL) will only be administered at baseline and several covariates will be assessed using chart and administrative data, reducing patient burden.

Study Measures for Patient Completion	Screening	Baseline	12 weeks	24 weeks
Screening Measures				
Patient Health Questionnaire (PHQ-9)	X			
Computer Literacy (study specific questions)	X			
Primary Outcome Measures				
Inventory of Depression Symptoms – Self Report (IDS-SR)		X	X	X
Veterans RAND 12-Item Health Survey (VR-12)		X	X	X
Quality of Life Enjoyment and Satisfaction Questionnaire		X	X	X
Recovery Assessment Scale (RAS)		X	X	X
Secondary Outcome Measures*/ Many also Mediators				
Depression Coping Self-Efficacy Scale (DCSES)		X	X	X
Cognitive-Behavioral Therapy Skills Questionnaire (CBTSQ)		X	X	X
Adherence with Antidepressant Medications (MPR* and BMQ)		X	X	X
Receipt of Traditional In-Person Psychotherapy		X	X	X
State Hope Scale (SHS)		X	X	X
Patient Activation Measure		X	X	X
Internalized Stigma of Mental Illness (ISMI)		X	X	X
Working Alliance with Peer Specialist (study specific questions)			X	X
Generalized Anxiety Disorder -7 (GAD-7)		X	X	X
Beck Scale for Suicidal Ideation (BSS)		X	X	X
Other Covariates				
Demographics		X		
Alcohol use (AUDIT-C)		X	X	X
Primary care provider mental health activity*		X		
Concurrent health services use (VA administrative data* and CSI)		X	X	X
Mental health and substance use comorbidities*		X		
General medical burden*		X		
Baseline social support (ISEL)		X		
Distance to VA facility (calculated by staff)*		X		

*calculated by staff, no burden on patient

E.11 Study Analyses

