Bivariate/Multivariate Analyses: We will evaluate bivariate associations between patients' treatment condition (PS-cCBT versus EUC) and the study outcomes to determine unadjusted measures of effect. We will also examine bivariate relationships between each of the potential covariates and the outcomes, and between each of the potential covariates and intervention group to assess possible confounders. Bivariate relationships between potential covariates will also be assessed for any collinearity in subsequent analyses.

Independent (Predictor) Variables	Dependent (Outcome) Variables
Treatment Group PS-cCBT vs Usual Care Potential Covariates Demographics Baseline measures of outcome variables Psychiatric comorbidities Study Site Social Support Prior to Enrollment General Primary Care Clinician Level of Depression Treatment Activity Distance to nearest VA facility	Primary Outcome Variables IDS-SR VR-12 Q-LES-Q-SF RAS Secondary Outcomes * Depression Coping skills (DCSES, CBTSQ) Antidepressant adherence Traditional psychotherapy use (contingent on symptoms) Hope Patient activation Anxiety Suicidal Ideation

* please note some secondary outcomes may be considered mediators in other study analyses

Effects At Each Assessment Time: Comparison at 24 weeks post-enrollment will be our primary comparison, but we will also assess patient outcomes to acute effects of the PS-cCBT intervention at 12 weeks. We will first obtain unadjusted differences in the outcomes between the two study groups with its associated 95% confidence interval. Comparisons of primary outcomes (IDS-SR, VR-12, Q-LES-Q-SF, RAS) between treatment groups at each assessment time will be accomplished using multiple regression models. Multiple regression models for each outcome variables will include the baseline values of the outcome variable as covariates to adjust for baseline differences, making the model analogous to analysis of covariance. We will also include two dummy variables for three sites and adjust for additional baseline covariates that show baseline imbalances in bivariate analyses.

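### E.11.d requires mediator change to come before outcome change but states no test of this, and its first-named model uses coping change to the same 24-week visit as the outcome, where reverse causation can look like mediation

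*Combined protocol and SAP*

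**What the plan says.** E.11.d first screens candidate mediators. A variable qualifies if it is associated with both intervention and outcome at P < .10 and if "changes in the mediating variable occur prior to changes in outcomes". The section does not say how that order will be checked.

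It then describes the model. For a primary outcome such as 24-week symptoms, "we will additionally include the change in depression coping score from baseline to 24 weeks", with antidepressant adherence over the same window joined by and/or. The expected sign of mediation is that "the variance in 24 week symptoms explained by the intervention group will be less once the depression coping scores" and adherence are in the model. No indirect effect and no confidence interval are mentioned.

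The section closes with a second version: "We will also consider change in depression coping score from baseline to 12 weeks", and/or 12-week adherence, because an early effect on these variables may have influenced the 24-week outcome. It does not say which version leads or what happens if they disagree.

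Elsewhere, E.6 states that "The PS-cCBT intervention and enhanced usual care (EUC) will be delivered over 12 weeks". The E.10 schedule collects the coping scales (DCSES and CBTSQ) and the IDS-SR at baseline, 12 and 24 weeks. E.11.b states that "Multiple regression models for each outcome variables will include the baseline values of the outcome variable as covariates".

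**The concern.** Coping and depressive symptoms are both self-reported at the same visits. If less depressed patients simply rate their coping higher, treatment that improves symptoms by any route will also raise coping scores. Adding 24-week coping change to a model for 24-week symptoms then absorbs part of the group effect, although coping did nothing. The plan would read that fall as mediation.

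The conclusion on mechanism is at stake: whether the program works by building coping skills. Because no lead version is named, the version that carries no information on time order could supply that conclusion. The point is limited to self-reported coping. Adherence, which is also measured from pharmacy records, was not examined.

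**Working it through.** **The plan's own figure.** E.13 gives a 0.4 SD effect, two-sided alpha .05, 90% power and 20% dropout. n per arm = 2 × (1.960 + 1.282)² / 0.4² = 131.3, so 132; 132 / 0.8 = 165 per arm, 330 in total. This reproduces. The documents give no figure for the mediation analysis.

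**Assumptions for the illustration (not in the documents).** Symptoms S have SD 1. The baseline-to-later symptom correlation is .5 and the 12-to-24-week correlation is .6. The arm effect is 0.4 SD at both visits. Coping at each visit depends only on symptoms at that visit (correlation −r) plus noise, so coping has no effect on symptoms. The noise at baseline and at follow-up correlates k (coping's own persistence).

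**Spurious share with the plan's 24-week change score.** Write S24 = 0.5·S0 − 0.4·T + e, with var(e) = 1 − 0.5² = 0.75.

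- Effect of arm on coping change: a = 0.4r.
- Effect of coping change on S24, given arm and S0: b = −0.75r / [0.75r² + 2(1 − k)(1 − r²)].
- Share = a·b / (−0.4) = 0.75r² / [0.75r² + 2(1 − k)(1 − r²)].

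| | r = .3 | r = .5 | r = .7 |
|---|---|---|---|
| k = 0 | .0675/1.8875 = .036 | .1875/1.6875 = .111 | .3675/1.3875 = .265 |
| k = .5 | .0675/.9775 = .069 | .1875/.9375 = .200 | .3675/.8775 = .419 |

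**Spurious share with 12-week coping, baseline coping and baseline symptoms entered.** The residual covariance of 12- and 24-week symptoms is .6 − .25 = .35. Share = 0.35r² / [0.75r² + (1 − r²)] = .032, .093 and .195. The 24-week model with the same covariates has 0.75 in place of 0.35 in the numerator, giving .069, .200 and .419. The ratio is .35/.75 = .47, so like for like the 12-week mediator roughly halves the share. At r = .5 the 12-week share is .15 × .25/.9375 = .04 if the 12-to-24-week correlation is .4, and .55 × .25/.9375 = .15 if it is .8.

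**The plan's sign.** In simulated trials of 264 completers with no mediation and k = 0, adding the 24-week change score shrank the group coefficient in 76%, 89% and 98% of trials. With k = .5 and a somewhat stronger 12-to-24-week link, the variance explained by group fell in 83%, 96% and 99%.

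**How often a 95% interval for the indirect effect would wrongly exclude zero** (simulation, 132 per arm; separate runs differ by a few points):

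| Analysis | r = .3 | r = .5 | r = .7 |
|---|---|---|---|
| 24-week change score, k = 0 | 9% | 25% | 51% |
| 24-week change score, k = .5 | 14% | 42% | 69% |
| 24-week coping, both baselines entered, k = 0 | 17% | 41% | 70% |
| 12-week coping, both baselines entered, k = 0 | 7% | 33% | 67% |

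When path b is also adjusted for 12-week symptoms, the rate falls to about 1% to 4% if symptoms are measured with reliability of about .92 or more. The least favourable corner of that range (r = .7, reliability .92) gave 5% to 7% in separate runs. At r = .7 with reliability .8 to .7 the rate is about 16% to 26%. E.9.a gives IDS-SR alpha "in the range of 0.92-0.94", but that is internal consistency, not the reliability of symptom state over 12 weeks.

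**The case against.** The strongest defence is that the plan already contains the lagged version, with the right reason, and the data for it are scheduled. Time order is also a separate screening condition stated before the model, so the 24-week regression is not offered as the test of order. Both points are fair. A reader might infer that the plan has no lagged mediator, or that the 24-week model by itself breaks the plan's condition; the text supports neither. What remains is that the condition has no stated test, no lead version is named, and reduced explained variance is the only stated evidence.

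A reader might also take the table's percentages as the error rate of the plan's own procedure. They are not. The plan has no interval, and a rate cannot be attached to a rule whose order condition has no test. The percentages show what an interval on the same model would do.

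It is also tempting to think that moving to 12 weeks cures the problem. It does not. At r = .5 and .7 the unadjusted 12-week model errs in about 33% and 67% of trials, against 25% and 51% for the plan's noisier change score with k = 0. Most of the protection comes from adjusting for 12-week symptoms.

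That adjustment has a price. Treatment lasts 12 weeks, so coping gains that relieve symptoms during treatment are a natural hypothesis, and the adjusted analysis removes them. In one set of simulations, not repeated independently, requiring both analyses to agree detected full mediation in only 5% to 6% of trials when all of it ran through 12-week symptoms. Statisticians would differ on making agreement mandatory, so it should guide interpretation only.

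**Conclusion.** The point holds for the secondary mediation aim as it concerns self-reported coping. The first-named model cannot show time order, and the stated sign of mediation appears when there is none. The spurious share is about 4%, 11% and 27% at r = .3, .5 and .7 if coping has no persistence of its own, and about 7%, 20% and 42% if persistence is .5. All correlations, the persistence and the reliabilities below .92 are assumptions, so the sizes are illustrative. The mismatch between the stated condition and the first-named model does not depend on them.

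Nothing here bears on the primary 24-week comparison or on the 330 patients. A reader who infers a threat to the main result would be going beyond the documents. The matter is worth settling before analysis, but it is not critical.

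**What to change.** 1. Name the 12-week mediator, with baseline mediator and baseline outcome as covariates, as the lead mediation model for the 24-week outcome.
2. Replace the reduced-variance reading with an indirect effect and its 95% confidence interval.
3. Report that effect both without and with 12-week symptoms in path b. Describe mediation as supported when the two agree, and as unresolved, not absent, when only the unadjusted interval excludes zero. Present this as guidance for interpretation, not as a mandatory decision rule.
4. Label the 24-week concurrent model as a descriptive association.
5. State that reverse causation and unmeasured common causes of coping and symptoms are reduced, not removed.

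The cost is plan wording and some extra analysis of measures already collected at baseline, 12 and 24 weeks. There are two scientific downsides. The adjusted version removes true mediation that acts through symptoms during treatment, and mediator changes that arise only after week 12 are missed.
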